## Non-graded Abnormalities

The following worst-case post-baseline abnormalities L, N or H will be determined per subject, per laboratory test and for each analysis period, using all non-missing post-baseline records (including unscheduled and FU visits):

- L = low: at least one post-baseline result is classified as L.
- N = normal: all post-baseline results are classified as N.
- H = high: at least one post-baseline result is classified as H.

If, for a subject, both L and H are reported, the subject will be counted twice in the table: once with a worst-case L and once with a worst-case H.

### 6.3.2.8. Hepatotoxicity

Hepatotoxicity will be investigated by tabulating the aspartate aminotransferase (AST) and alanine aminotransferase (ALT) values categorized as  $>3$ ,  $>5$ ,  $>10$  and  $>20$  times their upper limit of normal (per analyte and over both analytes combined), ALP categorized as  $> 1.5$  times the upper limit and total bilirubin as  $> 2$  times the upper limit of normal. Elevations of AT (AST or ALT)  $> 3$  times their upper limits accompanied by elevated total bilirubin ( $>1.5 \times \text{ULN}$ ,  $>2 \times \text{ULN}$ ) on the same day will also be tabulated.

To assess the potential of the drug to cause severe liver damage, possible Hy's Law cases will be identified. These subjects are defined as having any elevated AT (AST or ALT) of  $>3 \times \text{ULN}$ , ALP  $<2 \times \text{ULN}$ , and associated with an increase in total bilirubin  $>2 \times \text{ULN}$  on the same day.

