11.1.4. Adverse Events of Special Interest

Not applicable.

11.1.5. Clinical Laboratory Abnormalities and Other Abnormal Assessments as Adverse Events or Serious Adverse Events

Laboratory abnormalities without clinical significance based on the investigator's judgment are not considered AEs or SAEs. However, laboratory abnormalities (e.g. clinical chemistry, hematology, and urinalysis) or other abnormal (clinical study-specific) assessments (e.g. ECG, radiography, vital signs) that require medical or surgical intervention, are associated with signs and/or symptoms, and/or lead to IP interruption, modification or discontinuation must be recorded as an AE or SAE if they meet the definition as described in Sections 11.1.1 and 11.1.2, respectively. If the laboratory abnormality is part of a syndrome, the syndrome or diagnosis is to be reported (e.g. anemia instead of decreased hemoglobin).

The following liver enzyme elevations must be reported as SAEs:

- AST or ALT $\geq 3 \times \text{ULN}$ with signs of liver damage (total bilirubin $> 2 \times \text{ULN}$ OR INR > 1.5 , and/or with the appearance of fatigue, nausea, vomiting, right upper quadrant pain or tenderness, fever, rash and/or eosinophilia [$> 5\%$]).

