Appendix 15: Algorithm for Elevated Liver Function Tests

	AST or ALT increase to				
Value Range	>=1.5x to 3xULN	>=3x to <5xULN	>=5x to <8xULN	>=3xULN with signs of liver damage ¹	>=8xULN
IP Action	Continue as planned	Reduce or interrupt IP for at least 2 weeks	Interrupt IP for at least 2 weeks	Discontinue IP ²	Discontinue IP ²
		Close observation ²	Close observation ²		
After at least 2 weeks	AST and ALT <3xULN	AST or ALT >=3xULN			
	Weekly LFTs for the first 2 weeks (biweekly for the following weeks, or more frequently at investigator's discretion)	Discontinue IP Report SAE and complete liver event page for any of abnormalities listed below ³ : - AST/ALT increase >=3xULN with signs of liver damage ¹			

¹ Signs of liver damage:

- total bilirubin >=2.0xULN OR INR >1.5, and/or
- symptoms: appearance of fatigue, nausea, vomiting, right upper abdominal quadrant pain or tenderness, fever, rash and/or eosinophilia (>5%)

² Close observation recommendations:

- Monitor 2 to 3 times per week all of the following parameters: ALT, AST, alkaline phosphatase, total bilirubin, eosinophils, INR. If local regulations allow, home visits can be performed if subjects cannot come to the clinical study center.
- Frequency of retesting can be reduced to once a week or less if abnormalities stabilize or the IP has been discontinued; however, monitoring might still be needed more frequently taking into consideration the SoC and/or changes to this.
- Based upon investigator's discretion gastroenterology or hepatology consultations, additional serology testing, imaging, and pathology assessments may be required.
- Re-query history of symptoms, prior and concurrent diseases, concomitant medication and non-prescription medicines, herbal, dietary supplements, alcohol use, recreational drug use, special diets.

- Rule out all of the following: acute viral hepatitis, autoimmune hepatitis, alcoholic hepatitis, non-alcoholic fatty hepatitis, hypoxic/ischemic hepatitis, biliary tract disease, and cholestasis.

- Re-query exposure to environmental chemical agents.

³ The following steps should be followed:

- The site should immediately contact the subject and require the subject to discontinue IP immediately. The subject should be asked to return to the site within a 48-hour window from awareness of the result.
- A full evaluation of various causes of hepatitis should be conducted (i.e. infectious, alcohol, medications, anatomical).

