## 1. INTRODUCTION

This statistical analysis plan (SAP) describes the final statistical analyses of study GLPG3970-CL-207. The results of the analysis will be described in the clinical study report (CSR).

Technical details on derivations and mock tables, listings and figures (TLFs) will be presented in a separate document.

The statistical analysis will process and present the results following the International Council for Harmonization (ICH) standards, particularly the ICH-E3, ICH-E6, ICH-E9, ICH-R9 (R1) and ICH-E14 guidelines.

On 26 November 2021, the Safety Monitoring Committee recommended to immediately terminate Study GLPG3970-CL-207 due to a safety signal of liver toxicity. Therefore, the GLPG3970-CL-207 study was prematurely stopped. In view of this, only the primary endpoint and safety analyses will be performed. Results will be presented in an abbreviated CSR. Any provisions no longer applicable following premature study termination are highlighted in grey.

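### The combined liver and possible Hy's Law rows count only same-day elevations, so bilirubin that first rises after AST/ALT has fallen to 3×ULN or below is not linked to it in any planned row

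*SAP*

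**What the plan says.** SAP 6.3.2.8 plans three kinds of liver summary.

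- **Single-analyte rows:** AST and ALT above 3, 5, 10 and 20×ULN, ALP above 1.5×ULN, and total bilirubin above 2×ULN.
- **Combined row:** AST or ALT >3×ULN with total bilirubin >1.5×ULN or >2×ULN. Pairs that occur "on the same day will also be tabulated" are the ones counted.
- **Possible Hy's Law:** AST or ALT >3×ULN with ALP <2×ULN, "associated with an increase in total bilirubin" above 2×ULN, again on one day. The SAP gives its purpose: "To assess the potential of the drug to cause severe liver damage, possible Hy's Law cases will be identified".

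SAP 6.3.2.9 turns these flags into a table of subject counts and percentages and marks them in the laboratory listing. SAP 6.3.2.1 restricts tables and figures to central-laboratory results; local results are only listed.

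SAP section 1 records that the Safety Monitoring Committee "recommended to immediately terminate Study GLPG3970-CL-207 due to a safety signal of liver toxicity", and that "only the primary endpoint and safety analyses will be performed". The liver summaries are therefore among the analyses that remain.

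**The concern.** Bilirubin and transaminases need not be abnormal on the same day. If bilirubin crosses its limit only after AST/ALT has come back to 3×ULN or below, the two findings belong to one subject but never share a date. The same happens if the two were never measured together by the central laboratory. Under SAP 6.3.2.8 that subject is not a combined case and not a possible Hy's Law case.

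The SAP treats other laboratory abnormalities differently. SAP 6.3.2.7 takes each subject's worst grade over all post-baseline records, including unscheduled and follow-up visits. Only the combined liver criteria depend on coincidence in time, and no look-ahead window, peak-against-peak table or sensitivity definition is given.

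The possible Hy's Law row is the SAP's stated screen for severe liver injury, and liver toxicity ended the trial. In a group this small, a reader will look at whether that row says zero or one.

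**Working it through.** The plan states no figure for this rule, so there is none to reproduce. The check applies the rule as written, asks when it misses a subject, and sizes one miss.

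**1. The rule on four illustrative profiles.** These are assumed, not trial data. ALP is <2×ULN throughout, and the 30-day look-ahead is also an assumption.

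| Profile | First draw (×ULN) | Later draw (×ULN) | Same-day rule | Look-ahead |
|---|---|---|---|---|
| A | Day 29: AT 10, bilirubin 1.0 | Day 36: AT 5, bilirubin 2.5 | counted | counted |
| B | Day 29: AT 10, bilirubin 1.0 | Day 43: AT 2.5, bilirubin 2.5 | not counted | counted |
| C | Day 29: AT 10, bilirubin 2.5 | none | counted | counted |
| D | Day 29: AT 6, bilirubin 1.2 | Day 57: AT 2, bilirubin 3 | not counted | counted |

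Profile A shows that a bilirubin rise after the transaminase peak is still counted if AST or ALT is above 3×ULN that day. Only B and D are lost.

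**2. Direction.** A same-day case is a look-ahead case with a lag of zero. The same-day count therefore cannot exceed the look-ahead count, and any difference goes one way.

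**3. How long the same-day opportunity lasts.** Assume AST/ALT falls exponentially from its peak. The time spent above 3×ULN is then half-time × log2(peak/3). The documents give no half-time, so a range of 2 to 14 days is assumed:

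- peak 4×ULN: 0.8 to 5.8 days
- peak 8×ULN: 2.8 to 19.8 days
- peak 10×ULN: 3.5 to 24.3 days

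Bilirubin must cross its limit, and be sampled, within that time to be counted.

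**4. Sampling.** Treatment visits are on Days 1, 8, 29, 57 and 85 (Protocol 5.1), so the gaps are 7, 21, 28 and 28 days. Close observation under Protocol Appendix 15 is denser: "Monitor 2 to 3 times per week all of the following parameters: ALT, AST, alkaline phosphatase, total bilirubin, eosinophils, INR". The same appendix lets retesting fall to weekly or less once values stabilise or the product is stopped. A miss is therefore possible, but its probability cannot be derived from the documents.

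**5. Size of one miss.** The planned active arm is 20 subjects (SAP 2.6). Exact Clopper-Pearson intervals are shown at 90%, the level the plan uses for its binary efficacy endpoint; the SAP plans no interval for these liver counts.

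- 0/20 = 0%; upper limit 1 − 0.05^(1/20) = 13.9%.
- 1/20 = 5%; lower limit 1 − 0.95^(1/20) = 0.3%; upper limit solves (1−p)^20 + 20p(1−p)^19 = 0.05, giving 21.6%.

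**The case against.** The case for leaving the SAP alone has several sound parts.

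- **The subject is not lost from the report.** Someone like profile D appears in the AST/ALT >3 and >5×ULN rows, the bilirubin >2×ULN row, the worst-case grade tables, the profile plots and the listings. If the event was reported as serious, it is also in the SAE listing and, if treatment-emergent, in the serious TEAE table (SAP 6.3.1.8). With 30 planned subjects, individual review is easy. This stands, and it limits the consequence to the two rows that join the elevations.
- **Close observation supplies same-day pairs.** It measures transaminases, ALP and bilirubin together several times a week. This stands while that frequency is kept.
- **The stakes are limited.** The committee had already acted on the liver signal, an abbreviated report is planned, and safety is summarised without formal testing (SAP 6.3). This also stands.

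A reader might infer more than the documents support:

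- *That any bilirubin rise after the transaminase peak is missed.* It is not, as profile A shows.
- *That the SAP contradicts the protocol.* Protocol 11.1.5 says "The following liver enzyme elevations must be reported as SAEs" and pairs AST/ALT ≥3×ULN with signs of liver damage; Appendix 15 uses similar wording. Neither gives a timing rule in either direction, so the protocol is silent rather than contrary. Those rules serve event reporting and product action, and they accept symptoms as a sign, which makes them broader than a biochemical screen.
- *That INR is ignored.* It is absent from SAP 6.3.2.8, but it is graded against baseline in SAP Appendix I and enters the worst-case tables.

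**Conclusion.** The point holds in a limited form and is a cheap improvement. Both joint liver criteria require coincidence on one day, and no other planned row connects a subject's transaminase and bilirubin elevations. The subjects affected are those whose bilirubin first passes its limit once AST/ALT is at or below 3×ULN, and those without a same-day central pair. The effect is an undercount in those rows, never an overcount relative to a look-ahead rule.

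One affected subject would move the active-arm figure from 5% to 0% at the planned 20. That figure assumes full enrolment; the study stopped early and the documents do not give the number treated. The decay times rest on assumed half-times. Nothing in the documents shows that such a subject existed or how likely one was, so it cannot be inferred that a case was missed or that the liver conclusion would change.

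**What to change.** In SAP 6.3.2.8, keep the same-day rows and add one row beside them: AST or ALT >3×ULN with total bilirubin >2×ULN on or after the AST/ALT elevation within a prespecified window, with ALP <2×ULN at the qualifying AST/ALT elevation. Thirty days is one possible window; it is an assumption, since neither document gives one. The same-day cases then form a subset of the new row.

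A display of each subject's peak AST/ALT against peak bilirubin, in multiples of ULN, would serve the same purpose. An extra row using INR >1.5, one of the protocol's signs of liver damage, is optional.

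The cost is a few lines of SAP text and a small programming change on data already collected. The downside is that an unrelated later bilirubin rise may be flagged and need a sentence of narrative. No clinical rule changes.

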### 6.3.2.9. Presentation of Results

Continuous laboratory tests including, glucose, cholesterol, triglycerides, low-density lipoprotein (LDL), high-density lipoprotein (HDL) and fasted glucose, will be summarized by means of descriptive statistics (including 90% CI of the mean change) by laboratory test, treatment group and analysis window. Actual values and change from baseline will be tabulated separately.

Profile line plots by subject of all actual observed values using relative day (ADY) and profile plots on change from baseline by analysis window will be presented by treatment group. All values, including unscheduled visits will be presented in profile plot. If there are more than one visits on the same day, time will be considered to order them. Graphs of the mean (+ SE) actual values over time and the mean (+ SE) change from baseline, and percent changes from baseline will be presented for all continuous laboratory parameters, with the exception of the metabolic markers.

The analysis of abnormalities will focus on assessments reported during the treatment period. Results reported before baseline will only be listed.

Non-graded abnormalities and toxicities grades of the actual values will be presented as shift tables of the worst-case abnormality/toxicity grade versus the baseline abnormality/toxicity grade. The table will be created per laboratory test, treatment group and analysis window. The results of non-graded abnormalities and toxicities grades will be shown separately.

A frequency table of the number (percent) of subjects with treatment-emergent worst-case abnormalities/toxicity grade per laboratory test, treatment group and analysis period will be presented. The results of non-graded abnormalities and toxicities grades will be shown separately.

A frequency table of the number (percent) of subjects will be also provided for hepatotoxicity flags defined before. These abnormalities will be also flagged in the individual data laboratory listing.

Listing will be provided for the laboratory test along with flag for abnormality results. In addition, pregnancy result will be listed separately.

### **6.3.3.      Electrocardiogram**

#### **6.3.3.1.     Available Data**

The following ECG parameters will be analysed: heart rate (HR), RR interval, PR interval, QRS interval, uncorrected QT interval, QTcF (derived).

#### **6.3.3.2.     Derivation Rules**

##### **Derived Parameters**

The Fridericia's cube-root corrected QT (QTcF) will be calculated using the following formula.

$$\text{Fridericia's cube-root corrected QT (Fridericia, 1920): } QTcF \text{ (ms)} = QT \text{ (ms)} \times \sqrt[3]{\frac{1000}{RR \text{ (ms)}}}$$

If RR is missing, then it will be derived from HR using the formula  $RR(ms) = 60000 / HR(bpm)$ .

##### **Handling of ECGs Measured in Triplicate**

If ECG is collected in triplicates, the following approach will be taken.

First, any derivation of ECG parameters will be done before handling ECG triplicates. Next, the mean of the triplicate ECG values will be calculated for each individual ECG parameter, without rounding the result. These calculated means will constitute the analysis values; any derivation (e.g. change from baseline, assignment of abnormalities) and statistic will be based on the mean value of the triplicates.

The values of the original members of a triplicate will be listed.

### 6.3.3.3. Abnormalities

The actual analysis values and changes from baseline of the QT and QTcF parameters will be categorized into the abnormality classes as defined in the SAP [Appendix II](#).

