8.5.4. Vital Signs

Vital signs (systolic and diastolic blood pressure, heart rate, and oral/tympanic body temperature, the same method of measuring body temperature to be used throughout the study) will be recorded in a standardized manner (i.e. after the subject has rested in a supine position for at least 5 minutes) at visits specified in the Schedule of Activities in Section 8.11 (see also Section 8.1, “[Timing of Assessments](#)”). Clinically significant abnormal values should be recorded as AEs.

8.5.5. 12-lead Electrocardiogram

At the time points specified in the Schedule of Activities (see Section 8.11 and also Section 8.1, “Timing of Assessments”), a 12-lead ECG will be recorded and results will be sent for central reading.

12-lead ECG recordings will be performed before blood sampling and after subjects rested for at least 5 minutes in supine position. In case an indwelling catheter is used, ECGs may be recorded after blood sampling, provided that there is at least 30 minutes between catheter insertion and the ECG recording. When catheter insertion would fail, the 12-lead ECG needs to be taken before the venipuncture and at least 30 minutes after the failed attempt. Triplicate ECGs (i.e. 3 ECGs) will be performed at Visit 1 (Day 1) predose and at 4.5 hours postdose, within a time span of 6 minutes, with an approximate 3-minute interval between ECGs. At all other timepoints, single ECGs will be taken.

The following parameters need to be recorded: heart rate, PR interval, RR interval, QRS interval, uncorrected QT interval, morphology, and rhythm analysis. QTcF will be derived. QTcF will be considered as normal if ≤ 450 ms, while a prolongation of QTcF to >500 ms and/or an increase from baseline >60 ms will be considered a threshold of concern.

Immediately after recording, the ECGs will be reviewed by the investigator to detect clinically significant abnormalities. This immediate review during the visit needs to be documented in the subject’s source. After receipt of the central report, also all flagged ECG abnormalities need to be assessed by the investigator on clinical relevance. Clinically significant abnormal findings should be recorded as AEs.

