#### Worst-Case Abnormality

The worst-case post-baseline categorized actual analysis value and the worst-case categorized change from baseline for QT and QTcF will be determined per subject, per parameter, and for each analysis period, using all non-missing post-baseline records (including unscheduled and FU visits).

The worst-case categorized actual analysis value is the category corresponding to the highest post-baseline actual value. In case of several equal highest post-baseline actual values, the earliest occurrence will be taken for the analyses and will be flagged in the listings.

The worst-case change from baseline is the category corresponding to the largest increase (positive change) from baseline. In case of several equal largest increase from baseline, the earliest occurrence will be taken for the analyses and will be flagged in the listings.

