**Table 8 Gradings for Urine Analysis Parameters**

Parameter	L1	L2	L3	L4	H1	H2	H3	H4
Urine erythrocytes	NA	NA	NA	NA	≥ULN	≥10 cells/HPF	NA	NA
Urine protein	NA	NA	NA	NA	1+ proteinuria	2+ and 3+ proteinuria; urinary protein <3.5 g/24 hrs	urinary protein ≥3.5 g/24 hrs; 4+ proteinuria	NA
Urine glucose	NA	NA	NA	NA	>ULN (presence of glucose)	NA	NA	NA

LLN: lower limit of normal, ULN: upper limit of normal, NA: not applicable.

Any laboratory parameter with treatment-emergent (i.e., worsening from baseline) abnormalities of grade 2 or above (ie, H2/L2 or higher/lower) should be considered a 'marked laboratory abnormality'. Marked laboratory abnormalities should be described in a corresponding section of the CSR as per ICH E3 guidance, section 12.4.2.3.

**Appendix II: Vital Signs and Electrocardiogram grading****Table 9 Gradings for Vital Signs and Electrocardiogram Parameters**

Parameter	L1	L2	L3	L4	H1	H2	H3	H4
Systolic blood pressure (mmHg)	<90	<60	NA	NA	NA	≥140	≥160	≥180
Diastolic blood pressure (mmHg)	<60	<45	NA	NA	NA	≥90	≥100	≥120
Heart rate (bpm)	<60	<50	<40	NA	>100	>115	>130	NA
Body temperature (°C)	NA	<35	NA	NA	>38	NA	NA	NA
Respiratory rate (breaths per minute)	<12	NA	NA	NA	>20	NA	NA	NA
O 2 saturation (%)	<95	<90	NA	NA	NA	NA	NA	NA
Weight	≥7% decrease from baseline	NA	NA	NA	≥7% increase from baseline	NA	NA	NA
QTc interval on ECG (ms)	NA	NA	NA	NA	>450	>480	>500	NA
QTc change from baseline (ms)	NA	NA	NA	NA	NA	>30	>60	NA
PR interval on ECG (ms)	<110	NA	NA	NA	>200	NA	NA	NA
QRS complex on ECG (ms)	<60	NA	NA	NA	>120	NA	NA	NA

Source: FRM-MED-005/006, valid on 08JUL2020.

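### SAP 6.3.3.3 sends uncorrected QT to an appendix with cut-offs only for QTc, and the PR and QRS grades in that appendix are never applied

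*SAP*

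**What the plan says.** SAP 6.3.3.1 lists the ECG parameters to be analysed: "heart rate (HR), RR interval, PR interval, QRS interval, uncorrected QT interval, QTcF (derived"). SAP 6.3.3.3 then restricts categorisation to two of them: "The actual analysis values and changes from baseline of the QT and QTcF parameters will be categorized into the abnormality classes" set out in Appendix II. The worst-case paragraph keeps the same pair: it covers the actual value, and "the worst-case categorized change from baseline for QT and QTcF will be determined per subject, per parameter, and for each analysis period". For actual values the worst case is the highest post-baseline value. For change it is the largest increase. Every abnormal change category counts as treatment-emergent. SAP 6.3.3.4 feeds these results into shift tables and treatment-emergent frequency tables by parameter.

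The ECG interval rows of Appendix II, Table 9 are:

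| Row label | Low | High |
|---|---|---|
| "QTc interval on ECG (ms") | none | >450, >480, >500 |
| "QTc change from baseline (ms") | none | >30, >60 |
| "PR interval on ECG (ms") | <110 | >200 |
| "QRS complex on ECG (ms") | <60 | >120 |

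There is no row for uncorrected QT or its change. Protocol 8.5.5 also works on the corrected interval: "QTcF will be considered as normal if" it is at most 450 ms, and its thresholds of concern are a QTcF above 500 ms or an increase above 60 ms. Protocol 9.3.5.6 promises frequency analyses of ECG abnormalities, on values and on changes, without limiting them to QT.

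**The concern.** There are two separate gaps.

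First, uncorrected QT shortens as heart rate rises, so a cut-off built for the corrected interval means something different at each heart rate. A table of raw-QT abnormalities on QTc limits would partly be a table of slow and fast hearts. Any treatment effect on heart rate would then appear as a QT effect, or hide one, in those rows. QT prolongation is named as an important potential risk in Protocol 5.5, so readers will look closely at this output.

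Second, Table 9 supplies PR and QRS grades and SAP 6.3.3.1 lists both intervals for analysis, but neither the categorisation rule nor the worst-case rule mentions them. A reader looking for the number of subjects with PR above 200 ms or QRS above 120 ms, by arm, is not told to expect one.

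**Working it through.** **Inputs.** The SAP 6.3.3.2 formula is QTcF = QT × (1000/RR)^(1/3), with RR = 60000/HR. Together these give QTcF = QT × (HR/60)^(1/3). The protocol's definition, QT/RR^(1/3) with RR in seconds, gives the same values (450 ms at 50 bpm is 423.5 ms by both). Cut-offs are those of Table 9. The plan states no figure to reproduce. The heart rates and intervals below are illustrative assumptions, because the documents give no heart-rate distribution.

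**Raw QT against the QTc value cut-offs.**
- QT 460 ms at 50 bpm: 460 × (50/60)^(1/3) = 432.9 ms. Raw QT is H1 and QTcF is ungraded.
- QT 390 ms at 100 bpm: 390 × (100/60)^(1/3) = 462.4 ms. Raw QT is ungraded and QTcF is H1.
- QT 440 ms at 90 bpm: 440 × (90/60)^(1/3) = 503.7 ms. Raw QT is ungraded and QTcF is H3.

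Conversely, hold QTcF at 440 ms, which is ungraded at every heart rate. Raw QT = 440/(HR/60)^(1/3) is then 484.3 ms at 45 bpm (H2), 467.6 ms at 50 bpm (H1) and 399.8 ms at 80 bpm (ungraded).

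**Raw QT change against the QTc change cut-offs.**
- QTcF constant at 420 ms, heart rate 75 to 60 bpm: QT goes from 420/(75/60)^(1/3) = 389.9 to 420.0 ms, a change of +30.1 ms (H2). The true QTcF change is zero.
- The same with 80 to 60 bpm: 381.6 to 420.0 ms, a change of +38.4 ms (H2).
- QTcF rising by 61 ms, from 420 to 481 (H3), while heart rate goes from 60 to 75 bpm: QT goes from 420.0 to 481/(75/60)^(1/3) = 446.5 ms, a change of +26.5 ms (ungraded).

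Because every abnormal change category is treatment-emergent, the first two of these would enter the raw-QT frequency table.

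**Where the PR and QRS grades are used.** Two body sections rely on Appendix II for ECG or vital signs.
- SAP 6.3.3.3 (ECG) names QT and QTcF only.
- SAP 6.3.4.3 (vital signs) covers the parameters listed in 6.3.4.1: weight, blood pressure, heart rate and temperature.

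Neither assigns a PR or QRS grade. The tables in 6.3.3.4 are described as by parameter, without saying whether PR and QRS are included. If they were simply added, the worst-case rule would still take only the highest value, so PR below 110 ms or QRS below 60 ms could be missed in a subject with other, higher readings. Table 9 has no change rows for PR or QRS, so only their actual values can be graded.

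**The case against.** The strongest reply is that nothing important is lost, and much of it stands.

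- **A reader might infer that QT prolongation would be missed.** The documents do not support that. QTcF is categorised in parallel for value, change and worst case, so the ECGs above with QTcF of 462 and 504 ms would be graded H1 and H3 there. Only the additional raw-QT rows are affected.
- **A reader might infer that conduction abnormalities go uncounted, or that PR and QRS appear only as means.** That is also too strong. Descriptive statistics include median, minimum and maximum (SAP 4.5.2). SAP 6.3.3.4 adds subject profile plots, a listing, and a frequency table of CRF ECG interpretations. Protocol 8.5.5 has clinically significant findings recorded as AEs. What is missing is a count against the Table 9 grades. The CRF table is by time point, is not described as worst-case or treatment-emergent, and may not isolate conduction findings. AE recording depends on the investigator's judgement.
- **A reader might infer an effect on treatment discontinuation.** There is none: decisions under Protocol 6.4 are made during the study and do not depend on an SAP table.
- **The SAP never says outright that raw QT takes the QTc cut-offs.** This is correct. It is an inference from there being no other QT row. The alternative is that raw QT has no class at all, which also needs correcting.
- **Unused rows are normal in this appendix.** Table 9 also grades respiratory rate and oxygen saturation, which SAP 6.3.4.1 does not list. The high-to-low wording in the ECG treatment-emergent rule also occurs in the laboratory rule. Neither therefore shows that PR and QRS grading was intended and then dropped. The gap against Protocol 9.3.5.6 does not depend on intent.

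**Conclusion.** Both gaps hold, and both are minor. The raw-QT categorisation is either undefined or, on the only available cut-offs, dependent on heart rate in its abnormality, shift and treatment-emergent rows. The PR and QRS grades exist but are not applied, so outliers are not counted against them, short of what Protocol 9.3.5.6 promises.

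The number of subjects affected cannot be calculated, because the documents contain no heart-rate, PR or QRS data. With about 30 subjects planned, individual plots and listings limit the harm.

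The conclusion assumes that a programmer following SAP 6.3.3.3 would use the QTc rows for raw QT. It also assumes that the ECG provisions remain in force after early termination. SAP section 1 keeps the safety analyses, but the grey shading that marks dropped provisions cannot be seen in the text available here.

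**What to change.** 1. In the first sentence of SAP 6.3.3.3 and in its worst-case paragraph, categorise QTcF only (value and change from baseline). Keep uncorrected QT in the descriptive statistics, plots and listing.
2. In the same two places, add PR and QRS actual values, graded by the existing Table 9 classes.
3. For PR and QRS, replace the highest-value-only rule with separate worst cases for low and high. A subject with both would be counted once in each direction, as SAP 6.3.2.7 already does for non-graded laboratory abnormalities.

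The cost is edits to two SAP paragraphs and a few extra rows in the existing shift and frequency tables. No new thresholds, data or clinical rules are needed.
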